During large measles outbreaks, WHO recommends using an MCV starting at 6 months to prevent measles among young infants. This dose of MCV should be considered only as MCV 0 dose and parents are advised to bring their infants to receive a routine MCV first dose at 9 months. Most studies of immunogenicity of measles containing vaccine in infants <9 months were conducted using a measles single antigen vaccine. There is a limited data on immunogenicity of MR vaccine administered at < 9 months of age and its impact on immunogenicity of MR vaccine routinely administered at 9 months. As more countries are introducing MR vaccine in their routine immunization program (at 9 months) we propose a study that will assess the immunogenicity of MR vaccine at 6 months (MCV 0 dose) and its impact on immunogenicity of MR vaccine administered at 9 months (MCV1 dose).

Relevance:

The primary purpose of the study is to assess the immunogenicity of MR vaccine when delivered at 6 months. In addition, the study will establish the equality of MR vaccine seroconversion administered at 9 months following administration of an earlier MR vaccine dose at 6 months of age compared to MR vaccine dose administered at 9 months without previous MR vaccination. This study will also provide additional data on safety and tolerance of MR vaccine given at 6 months, and impact of maternal antibodies on immunogenicity of MR vaccine at 6 months.

Hypothesis:

Our study hypothesis is that the proportion of children seroconverting after administration of MR vaccine dose at 9 months, and who had received an MR vaccine dose at 6 months of age, is not different from that obtained after administration of MR vaccine dose at 9 months in infants who had no previous dose of MR vaccine.

Primary objectives:

1. To assess immunogenicity of MR vaccine at 6 months of age
2. To assess immunogenicity of MR vaccine at 9 months of age among children without prior measles and rubella vaccination, compared with MR vaccine immunogenicity among those who had a prior MR vaccination at 6 months of age

Secondary objectives:

1. To assess the frequency of adverse reactions following administration of MR vaccine at 6 months
2. To compare the immunogenicity of the MR vaccine first dose administered at 6 months vs at 9 months.
3. To assess the proportion of mothers with undetectable, detectable and protective levels of measles and rubella antibodies

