Our study hypothesis is that the proportion of children seroconverting after MR vaccine dose at 9 months following administration of an earlier MR vaccine dose at 6 months of age (Arm A) is not different compared with the immunogenicity obtained when MR vaccine dose is administered at 9 months to infants who have had no previous dose of MR vaccine (Arm B). A secondary hypothesis is the incidence and spectrum of adverse reactions following immunization will be similar between doses given at 6 and 9 months (Arm A), and at 9 months.

The following questions are to be answered by the study:

1. What is immunogenicity of MR vaccine at 6 months of age?
2. What is the impact of the 6-month MR dose on immunogenicity of the 9-month MR dose?
3. What are the frequency and severity of adverse reactions following MR vaccination at 6 months and 9 months?
4. What is correlation between the measles and rubella antibody levels in mothers and level of maternal antibodies in infants

Specific Objectives

Primary objectives

1. To assess immunogenicity of MR vaccine at 6 months of age
2. To assess immunogenicity of MR vaccine at 9 months of age among children without prior measles and rubella vaccination, compared with MR vaccine immunogenicity among those who had a prior MR vaccination at 6 months of age

Secondary objectives:

1. To assess the frequency of adverse reactions following administration of MR vaccine at 6 months
2. To compare the immunogenicity of the MR vaccine first dose administered at 6 months vs at 9 months.
3. To assess the proportion of mothers with undetectable, detectable and protective levels of measles and rubella antibodies

4. To determine the extent of variation in measles antibodies in a convenience sample of women of child bearing age in a population with a long standing measles vaccination program
5. To determine the extent of variation in rubella antibodies in a convenience sample of women of child bearing age in a population where rubella vaccine have been recently introduced
6. To determine if variation in antibody levels in infants at 6 months is predominately explained by variation in starting antibody levels in the mother in this population
7. To estimate the half-life of decay of measles and rubella antibodies in infants

Background

Measles

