This study will be an open-label, randomized, 2-arm clinical trial. 620 children will be enrolled and randomized at 6 months of age to one of two study arms. The primary objectives of this study are to assess the immunogenicity of MR vaccine at 6 months, and assess equality of MR vaccine seroconversion administered at 9 months following administration of an earlier MR vaccine dose at 6 months of age compared with MR vaccine dose administered at 9 months only without previous MR vaccination. The study will enrol generally healthy 6 month old infants living in Matlab and who have never received an MR vaccine dose and have no history of measles or rubella. Participants will be followed to 11 months of age.

Infants in this study will be randomly assigned to one of two arms. Infants in Study Arm A will receive MR vaccine at 6 months of age (at enrolment) and at 9 months. Infants in Study arm B will receive MR vaccine only at 9 months.

Blood specimens will be collected from all infants at 6, 9 and 11 months of age. The 6 month sample is a pre-vaccination sample and mainly will be used to determine maternal antibody levels. For arm A, the sample collected at 9 months before the second MR dose will be used to assess antibody levels after the first MR dose at 6 months of age. For study Arm B, the 9 month sample will be used to assess measles and rubella antibody decay rate. The sample collected at 11 months will be used to assess immune response to either a two dose or a one dose schedule (arms A and B, respectively). The study design and participant evaluations are illustrated in the Table.

Table: Schematic representation of study arms

Arm		Age of participant				
		6 months	9 months	11 months	Sample size	Enrollment target (sample size + 10% attrition)
A	MR 6 & 9 months	MR •	MR •	•	279	310
B	MR 9 months	•	MR •	•	279	310
	Total (infants)				558	620
	Mothers	•			558	620

• Indicates blood collection
MR- Measles -rubella vaccination

Blood specimens will be collected from mothers of all enrolled infants at time of enrolment.

Study enrolment and withdrawal

A sample of 620 infants at age 6 months (180 days, +/- 7 days) of age (310 per each study arm) will be enrolled from population living in Matlab area. Inclusion and exclusion criteria are provided below.

Inclusion criteria: Infants

- Healthy infants at 6 months (180 days, +/- 7 days) of age (calendars will be provided to staff)

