For participants in the study group A, the immune response to the 6 month MR dose will be measured at 9 months (blood drawn during the second visit) to evaluate both the proportion seroconverting (from negative to protected), 4-fold or greater increase in antibody titers among pre-vaccination seropositives, after adjusting for decline in maternal antibodies, as well as the magnitude of the immune response (expressed as geometric mean titers of the antibody response). The rate of decay of maternal measles and rubella antibodies will be calculated in infants in arm B based on the difference of antibody levels measured at 6 months (baseline) and 9 months. We will incorporate the model of maternal measles and rubella decay for infants in arm A to measure post-vaccine antibody levels and impact of the maternal

antibody to immune response in infants who had measles or rubella antibodies at enrolment. In the recently published study from Bangladesh, baseline measles virus serum neutralizing antibody seroprotection and anti-rubella virus IgG seroprotection at 9 months of age was low (0.42-1.25% and 0-0.42%, respectively) (21). If during this study, we determine that most children have no detectable levels of maternal measles or rubella antibodies at 6 months it would be impossible to calculate the decay. In this case, we will refer to antibody decay rates reported elsewhere (29, 30).

THE FOLLOWING CHANGES ARE MADE TO THE PROTOCOL:

Since the inception of the project and completion of the field data collection a newer assay, multiplex bead assay (MBA) for measles and rubella has been developed. It has been validated by the CDC measles and rubella laboratories.

Multiplex Bead Assay (MBA) for Serum Antibody Detection of Measles and Rubella

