Frozen sera will remain frozen during routine shipments to the laboratory at icddr,b and to the CDC measles/rubella laboratory in Atlanta. Shipment of serum will be made according to internationally recognized standards for transport of specimens.

Long-term specimen storage

The parents will be requested to permit storage of blood specimens for no more than 5 years for potential future use in studies. All specimens will be destroyed after 5 years from the end date of the study (the date of last study visit of the last participant to be enrolled). Specimens will be destroyed as per standard procedures of the laboratory for destruction of biohazardous waste.

Sample Size Calculation and Outcome (Primary and Secondary) Variable(s)

Sample size

The study will be powered to address the primary objectives. Sample size calculations are based on equality comparisons with 10% attrition.

Assuming 50% MR seroconversion to a dose at 6 months of age, a sample size of 271 per arm will provide a precision of +/-5% with a 0.90 probability of obtaining an estimate within the desired range. Adjusting for 10% attrition, the enrolment target is 302. Assuming a seroconversion for measles of 75% following a single dose given at 9 months of age, a seroconversion of 65% for a 9 month dose preceded by a 6 month dose, and power of 80%, a sample size of at least 279 per arm is required. Adjusting for 10% attrition, this sample size is inflated to 310. The overall study samples size will be 620 infants. 620 mothers of infants will also be enrolled. (Table)

Time to endpoint (and the corresponding objective)

Primary endpoint

- Time from randomization at 6 months to collection of blood at 9 months of age (To assess immunogenicity of MR vaccine at 6 months of age)
- Time from randomization to collection of blood at 11 months of age (To assess immunogenicity of MR vaccine at 9 months of age among children without prior measles and rubella vaccination, compared with MR vaccine immunogenicity among those who had a prior MR vaccination at 6 months of age)

Secondary endpoint

- Time from randomization 11 months (To assess the frequency of adverse reactions following administration of MR vaccine at 6 months)
- Time from randomization to 11 months of age (To compare the immunogenicity of the MR vaccine first dose administered at 6 months vs at 9 months)

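### The plan aims to establish equal seroconversion after the 9-month dose, but its only between-arm test is a chi-square for a difference, with no margin, interval rule, alpha or sidedness

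*Combined protocol and SAP*

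**What the plan says.** **Aim.** Under Relevance in the Project Summary, "the study will establish the equality of MR vaccine seroconversion administered at 9 months" with and without an earlier 6-month dose. Study design repeats this as a primary objective, to "assess equality of MR vaccine seroconversion administered at 9 months". The section Hypothesis to be tested predicts that seroconversion in Arm A "is not different compared with the immunogenicity obtained when MR vaccine dose is administered at 9 months" to infants with no earlier dose.

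**Sizing.** The Sample size section states: "Sample size calculations are based on equality comparisons with 10% attrition". It assumes 75% measles seroconversion after a single 9-month dose and 65% when a 6-month dose came first, and concludes: "and power of 80%, a sample size of at least 279 per arm is required". Attrition of 10% raises this to 310.

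**Analysis.** The list that closes the analytical approach compares proportions between arms by chi-square for statistical significance. The combined document contains no equivalence or non-inferiority margin, no between-arm confidence interval, and no alpha or sidedness for this test.

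**Status of the endpoint.** The Primary endpoint list includes "Time from randomization to collection of blood at 11 months of age" for the between-arm objective. The later Secondary outcomes list places the 11-month titres among the secondary outcomes.

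**The concern.** The aim and the test point in different directions. A chi-square can provide evidence that two proportions differ. When it is not significant, it does not show that they are the same, because the data may still be compatible with a material loss. The plan never says that non-significance will be read as equality, but it gives no other route to that conclusion.

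The trial asks whether an early dose blunts the response to the routine one. A false reassurance is therefore the error that matters most, and the stated power cannot be interpreted without the level it belongs to.

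The point concerns the 11-month comparison only. The analysis list also tests seroconversion at 9 months. If that means the 9-month visit, Arm B is still unvaccinated ("For study Arm B, the 9 month sample will be used to assess measles and rubella antibody decay rate"), and equality is not the question there.

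**Working it through.** **Inputs from the Sample size section:** Arm B 75%, Arm A 65%, difference d = 0.10, power 80% (z = 0.8416), 1:1 allocation, 279 per arm. Alpha is not given, so two levels are tried.

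**1. Reproducing 279.** Pooled formula, with mean proportion 0.70:

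n = [z_α √(2 × 0.70 × 0.30) + z_β √(0.75 × 0.25 + 0.65 × 0.35)]² / d²

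- Two-sided 5%: (1.960 × 0.6481 + 0.8416 × 0.6442)² / 0.01 = 328.5
- Two-sided 10%: (1.645 × 0.6481 + 0.8416 × 0.6442)² / 0.01 = 258.6

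Continuity correction: n′ = (n/4) × [1 + √(1 + 4/(n d))]².

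| Level | Pooled | Pooled, corrected | Unpooled | Unpooled, corrected | Arcsine |
|---|---|---|---|---|---|
| Two-sided 5% | 328.5 | 348.2 | 325.7 | 345.4 | 327.6 |
| Two-sided 10% (one-sided 5%) | 258.6 | 278.26 | 256.6 | 276.2 | 258.0 |

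Only 278.26 rounds up to 279, and 279 / 0.9 = 310 matches the enrolment target. The same section's precision calculation also fits a 90% level: 1.645² × 0.25 / 0.05² = 270.6, which gives its 271. This is a back-calculation; the documents do not say how 279 was obtained.

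**2. Power and missed losses at 279 per arm.** Exact binomial enumeration of the chi-square, Arm B at 75%, uncorrected (continuity-corrected in brackets). The 7-point loss is an assumption of this review.

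| | Two-sided 5% | Two-sided 10% |
|---|---|---|
| Power, true 75% v 65% | 73% (70%) | 83% (80%) |
| Non-significant, true 10-point loss | 27% (30%) | 17% (20%) |
| Non-significant, true 7-point loss | 55% (59%) | 42% (46%) |

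With no attrition (310 per arm), power for 75% v 65% at two-sided 5% is 78% (75%).

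**3. What a non-significant result can hide.** Arm B is set at 209/279 = 74.9%, and the largest loss that stays non-significant (uncorrected) is taken.

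- Two-sided 5%: 189/279 in Arm A, difference −7.17 points. Pooled proportion 398/558 = 0.713, SE = √(0.713 × 0.287 × 2/279) = 0.0383, z = 1.87, p = 0.061. The 95% Wald interval is −7.17 ± 7.48, so it reaches a loss of 14.6 points.
- Two-sided 10%: 192/279, difference −6.09 points, p = 0.11. The 90% interval reaches a loss of 12.3 points.

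Continuity correction only raises these p-values, so both examples stand with it.

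**4. Precision available.** With 75% in both arms, the half-width is z √(2 × 0.75 × 0.25 / 279): 7.2 points at 95% and 6.0 points at 90%.

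**The case against.** Equality is the ordinary label for a test of p1 = p2. On that reading the sizing and the chi-square agree with each other, and the numbered primary objectives are neutrally worded. Only the Relevance section promises to establish anything. This explains how 279 and the test came about. It does not justify the Relevance wording or a research hypothesis of no difference.

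The precision calculation hints that a 90% level was used throughout. If so, 80% power is right with continuity correction, and the 73% figure applies only to a reader or analyst who uses two-sided 5%. That is fair: the power restatement is conditional, and the level simply has to be disclosed. The main problem remains at either level.

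The worked examples sit at the unfavourable edge. With Arm B at 209/279, an observed loss of up to 7 infants (2.5 points) still gives a 95% interval that excludes a 10-point loss; for the 90% interval the limit is 10 infants (3.6 points). If the arms are truly equal at 75%, about 79% of non-significant results at two-sided 5%, and 90% at two-sided 10%, exclude a 10-point loss. At a true 7-point loss the shares are only 22% and 46%. The interval separates these cases and the p-value does not, which is the reason to require one.

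The primary-or-secondary status of the 11-month result is a separate inconsistency. It needs reconciling but adds no weight here.

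**Conclusion.** The concern holds. As written, the plan's only route to its stated conclusion is a non-significant difference test. Such a result is compatible with a loss larger than the 10 points used for sizing, whether the level is two-sided 5% or 10%, with or without continuity correction. The figure of 279 is sound arithmetic under an undisclosed level; at two-sided 5% its power is about 73% (70% corrected).

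These figures rest on the protocol's 75% for Arm B and 279 evaluable infants per arm. The examples use a chosen count of 209 in Arm B, and the 7-point scenario is illustrative. The documents support no particular margin. This should be fixed, because it changes what the trial may conclude.

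**What to change.** 1. In the Sample size section, state the alpha, sidedness and formula actually used for 279, and apply the same level to the 11-month between-arm test. If that test is two-sided 5%, restate the power at 279 as about 73% (70% corrected).
2. For the 11-month comparison, report the Arm A minus Arm B difference in seroconversion with a confidence interval at the matching level. State that equality will not be concluded from a non-significant chi-square.
3. Choose one of two courses. Either reword Relevance, the hypothesis statements and Study design as a comparison sized to detect a 10-point difference. Or keep a claim of not different (or not worse) only if the interval excludes a margin that the sponsor justifies and records, with a date, before the arms are compared on serology; otherwise report that a difference has not been excluded. The 10 points in the Sample size section is not a margin by default. If serology by arm has already been seen, only rewording is left.
4. Reconcile the Primary endpoint and Secondary outcomes lists on whether the 11-month comparison is primary.

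**Cost.** Wording, plus a dated margin if that course is taken. The protocol change notice refers to the time "Since the inception of the project and completion of the field data collection a newer assay" was developed, so field work is over and the sample is fixed. The Data safety monitoring board section says sera are analysed after field work, and the documents do not show whether the arms have been compared. Expected intervals of about ±7.2 points (95%) or ±6.0 points (90%) limit which margins could be excluded, and the restated power may look less favourable.

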2. A study doctor will obtain a medical history and conduct a medical examination to assess whether the infant is eligible to take part in the study.
3. Infants who are not eligible per inclusion and exclusion criteria will be excused from study participation and it will be documented in the case reporting form.

4. Participants who meet temporary exclusion criteria at enrollment will be excused for the day and will be requested to return several days later, but as long as their age is 180 days, +/- 7 days. A note will be made in the case reporting form.
5. The eligible infant will be given a study ID and assigned to a study arm (arm A or B) according to a pre-determined randomization scheme. Further details of the randomization scheme are described in the 'Data Analysis' section.
6. Parents will be interviewed and socio-demographic and clinical information will be collected as per standardized study questionnaire.
7. One blood specimen (minimum of 1 ml) will be collected by venipuncture from all enrolled infants following the enrollment. During visits in which the child receives vaccine, blood samples will be drawn before vaccine administration.
8. One blood specimen (1 ml) will be collected by venipuncture from mothers of all enrolled infants following the enrollment.
9. Infants randomized to the study arm A will be administered the first dose of MR vaccine. Vaccine will be administered only if an adequate blood specimen has been collected from the participant.
10. The participant will be observed for 30 minutes for any adverse reactions from administration of the vaccine or the blood collection.
11. A research assistant will schedule the second visit. All participants will be requested to return 3 months later after enrolment, i.e., at 9 months of age.

Follow up home visit (2 days after MR vaccination). Safety monitoring.

- Children in study arm A, who received a 6 month dose of MR vaccine, will be visited by a field research assistant at their homes 2 days after MR vaccination. This visit is to identify if any participants experienced any adverse events following immunization.
- The research assistant will inquire about and record any potential adverse events after the 6 month dose of MR. All finding will be captured in the AEFI form.

Study site visit at 9 months of age. Blood draw and MR vaccination.

During the 9 month visit, the following procedures will be conducted:

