- Collection of blood from mothers at time of enrolment to assess measles and rubella titers, as only one blood sample will be collected. (To assess the proportion of mothers with undetectable, detectable and protective levels of measles and rubella antibodies)
- Time from randomization to 9 and 11 months (To assess the correlation between measles and rubella antibody levels in women and levels of maternal antibodies in infants)
- Time from randomization to 9 months, Arm B (To estimate the half-life of decay of maternal measles and rubella antibodies in infants)

The primary end-point assessment is based on measles titers by MBA (mIU/ml) and rubella titers (IU/mL) by ELISA on sera collected 12 weeks after the first dose (time between 6 and 9 months) and 8 weeks after completion of vaccination (time between 9 and 11 months). Immune response is defined as a 4-fold increase in antibody titers 12 weeks after vaccination (post-6-month visit) compared with 6-month pre-vaccine titers accounting for the expected decline in maternal antibody titers or a change from antibody-negative to positive (i.e. seroconversion). However, quantitative data (i.e., determining titers) will allow seroconversion defined by other -fold increases to also be assessed.

We will calculate the rate of decay for those infants that have maternal antibodies detected at enrolment (at 6 months) in arm B (anti-measles or anti-rubella IgG levels at 6 months vs 9 months). We will incorporate the model of maternal decay for infants in arm A to measure post-vaccine antibody levels and impact of the maternal antibody to immune response. However, if we determine that most children have no detectable levels of maternal measles or rubella antibodies at 6 months it would be impossible to calculate the decay rate (in Arm B). In this scenario, we will refer to antibody decay rates reported elsewhere (29, 30).

Outcome measures/variables:

The primary end-point assessment is based on measles titers by MBA (mIU/ml) and rubella titers (IU/mL) by ELISA on sera collected 12 weeks after MR 6-month dose of vaccination (i.e., at 9 months) for study Arm A.

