- Compare the proportion of participants demonstrating seroconversion at 9 months in both study arms. We will use chi-square test to test for statistical significance
- Compare the change in median titers of measles and rubella antibodies by study arm
- Compare immunogenicity of MR vaccine administered at 6 months (Arm A) vs 9 months (Arm B). Analyse the relationship of infants' immunogenicity to MR vaccine and mothers' level of antibodies
- Analyse the relationship between the levels of infants' maternal measles and rubella antibodies and mothers' antibodies
- Analyse results of adverse events by study arm and compare by age and arm of the study.

Data Safety Monitoring Plan (DSMP)

Records to be kept

Participant data will be collected using case report forms (CRFs). Personal identifiers will not be recorded on any CRFs, biological specimens or electronic records. Participants will be identified by a participant identification number (PID), which will be provided after enrolment and randomization. The PID will be used to link information recorded in CRFs and results from laboratory analysis of biological specimens.

Data entry, cleaning and storage

Records of participants will be kept in a locked cabinet with access restricted to study staff and investigators. All computer records will be kept in a locked room. The computers will be password protected. Only the study staff and investigators will be authorized to access the digital records.

Data from the CRFs will be entered into an electronic database. Checks will be performed to identify and correct data entry errors. After the completion of analysis and publication of study results, the study forms and database will be archived. The forms will be stored in a locked cabinet with access restricted to investigators. The database will be password protected.

Site monitoring plan

Prior to start of the study, Standard Operating Procedures (SOPs) will be developed by investigators in consultation with study staff. Study staff will be trained in study procedures and human subjects' management. After start of the study monitoring of study site will be conducted twice.

During these monitoring visits the following study documents and procedures would be reviewed:

1. Participant records, including consent forms
2. CRFs and other supporting data
3. Adverse event forms
4. Data Safety and Monitoring Board (DSMB) reports
5. Laboratory specimen records
6. Vaccine and biological materials storage and records

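### The mother–infant antibody correlation is timed at 9 and 11 months, mostly post-vaccination samples, which contradicts the plan's own use of the 6-month sample for maternal antibody

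*Combined protocol and SAP*

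**What the plan says.** The secondary end-point list in the section Time to endpoint (and the corresponding objective) reads "Time from randomization to 9 and 11 months (To assess the correlation between measles and rubella antibody levels in women", and the line goes on to name infants' maternal antibody as the other variable. No arm is specified and the 6-month sample is not mentioned. The next line, on the half-life of maternal antibody, is limited to Arm B up to 9 months.

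Other parts of the plan point to 6 months:

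- Secondary objective 6 is "To determine if variation in antibody levels in infants at 6 months is predominately explained by variation in starting antibody levels in the mother".
- Study design states: "The 6 month sample is a pre-vaccination sample and mainly will be used to determine maternal antibody levels".
- General analytical issues takes the 6-month titre as the baseline from which maternal antibody declines.
- Primary analytical approach ties the presence of maternal antibody to the 6-month specimen.
- Potential risks to participants says that the 6-month draw establishes baseline maternal titres in both arms.

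The list of analyses that closes the Data Analysis section contains "Analyse the relationship between the levels of infants' maternal measles and rubella antibodies and mothers' antibodies" and names no visit. A separate item there relates infants' vaccine response to mothers' antibody.

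**The concern.** Secondary objective 6 asks how far the antibody an infant holds at 6 months follows the mother's level. A sample taken after vaccination does not answer that, because infant IgG then contains the infant's own response. The protocol also says, under Response to early vaccination and Study Rationale, that maternal antibody can neutralise vaccine virus. Infants of high-titre mothers may therefore respond less well, which pushes the correlation in vaccinated samples downwards.

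An analyst who followed the end-point line literally could report that infants' maternal antibody hardly tracks the mother's level, or tracks it inversely, when the data show vaccine response.

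**Working it through.** **1. Vaccination status of each sample.** Study design gives Arm A a dose at 6 and at 9 months, and says "Infants in Study arm B will receive MR vaccine only at 9 months". The enrolment-visit procedures state: "During visits in which the child receives vaccine, blood samples will be drawn before vaccine administration". Study design says of Arm A's 9-month sample that it "will be used to assess antibody levels after the first MR dose at 6 months of age", and it assigns the 11-month sample to vaccine response in both arms. Hence:

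| Sample | Arm A | Arm B |
|---|---|---|
| 6 months | before any dose | before any dose |
| 9 months | after dose 1 | before any dose |
| 11 months | after dose 2 | after dose 1 |

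The end-point line covers the two lower rows, and 3 of those 4 cells are post-vaccination. At the enrolment target of 310 per arm that is 3 × 310 = 930 of 4 × 310 = 1,240 infant samples.

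**2. Can the assays separate the two sources?** The multiplex bead assay is described as detecting antibody raised by vaccination or by natural infection. Possible limitations concedes that laboratory methods cannot tell maternal from post-infection antibody. The plan describes no method for separating maternal from vaccine-induced IgG in a sample.

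**3. Illustrative size.** The plan gives no expected correlation, sample size or precision for this analysis, so there is no figure to reproduce. A simulation of 400,000 mother–infant pairs on the log2 scale shows the pattern.

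From the Sample size section: response probabilities p0 of 50% (dose at 6 months), 75% (Arm B at 9 months) and 65% (Arm A at 9 months). All other inputs are assumptions:

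- Mother: M ~ Normal(log2 1000, SD 1.5).
- Infant: I6 = M - 180/h + Normal(0, SD 0.7); I9 = I6 - 90/h + Normal(0, SD 0.3); I11 = I9 - 60/h; half-life h = 30 or 45 days.
- Response: log-odds = logit(p0) - s·c, where c is the pre-dose maternal log2 titre minus the mean of I6.
- Responder's vaccine log2 titre = 9.5 - b·c + Normal(0, SD 1.2).
- Responders carry vaccine plus residual maternal antibody. Non-responders carry residual maternal antibody only. Arm A at 11 months takes the higher of its first-dose result and its second-dose vaccine titre.
- Blunting (s, b): none (0, 0), weak (0.3, 0.2), moderate (0.6, 0.3), strong (1.0, 0.5).
- No detection limit is applied.

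Closed-form check at 6 months: Pearson = 1.5/√(1.5² + 0.7²) = 1.5/1.655 = 0.906; Spearman = (6/π)·arcsin(0.906/2) = 0.90. For Arm B at 9 months: 1.5/√(1.5² + 0.7² + 0.3²) = 1.5/1.682 = 0.892, giving Spearman 0.88. Both agree with the simulation.

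Spearman correlation with the mother's titre (h = 30 / h = 45):

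| Blunting | 6 mo, both arms | B at 9 mo | A at 9 mo | Pooled 9 mo | A at 11 mo | B at 11 mo | Pooled 11 mo |
|---|---|---|---|---|---|---|---|
| None | 0.90 / 0.90 | 0.88 / 0.88 | 0.22 / 0.24 | 0.50 / 0.50 | 0.03 / 0.03 | 0.05 / 0.07 | 0.04 / 0.05 |
| Weak | 0.90 / 0.90 | 0.88 / 0.88 | -0.02 / 0.00 | 0.39 / 0.40 | -0.31 / -0.30 | -0.24 / -0.23 | -0.27 / -0.26 |
| Moderate | 0.90 / 0.90 | 0.88 / 0.88 | -0.19 / -0.18 | 0.31 / 0.32 | -0.43 / -0.45 | -0.37 / -0.36 | -0.40 / -0.41 |
| Strong | 0.90 / 0.90 | 0.88 / 0.88 | -0.35 / -0.34 | 0.24 / 0.24 | -0.56 / -0.59 | -0.51 / -0.52 | -0.53 / -0.56 |

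Because c is centred on the 6-month mean, the realised Arm B response exceeds 75% once blunting is switched on (83% to 95%). That is a further reason to read the table for direction only.

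**The case against.** **The 6-month sample is implied.** Randomization takes place at the 6-month visit, so an interval starting there may be meant to include that sample. The half-life line also does not name it, yet the text that follows uses 6 against 9 months. This is a fair reading of loose wording. It still leaves the line running on to vaccinated samples in both arms, without the Arm B limit that its neighbour has.

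**The timing is fixed elsewhere.** Objective 6 and the Primary analytical approach do point to 6 months, and the variable is named as maternal antibody, so a careful analyst may well choose the right visit. This stands, and it makes the defect an internal contradiction. Study question 4, whose correlation wording the line follows, gives no age and does not resolve it.

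**The decay model could isolate maternal antibody.** The plan uses that model to judge the vaccine response. Under the fixed decay rate stated in Potential risks to participants, a projected titre is the 6-month titre times a constant over a common interval. Its rank correlation with the mother is then the 6-month one, and later visits add nothing.

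**Stronger readings that the documents do not support.** A reader might infer that nothing on the line measures maternal antibody. Arm B at 9 months does, since it is bled before its dose. A reader might also infer from Special Assays or Procedures that almost no maternal antibody is left by then. The figures there (0.42-1.25% for measles, 0-0.42% for rubella) are percentages above a protective threshold in an earlier trial, and titres below it may still be measurable and ranked. Finally, a reader might infer that the correlation must turn negative. Without blunting it does not, and pooled 9-month data stay positive in every scenario.

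**Conclusion.** The point holds as an internal contradiction in the timing of one secondary analysis. Followed as written, three of the four arm-by-visit groups would describe vaccine response mixed with residual maternal antibody. The correlation would be attenuated at 9 months when the arms are pooled, and essentially lost at 11 months even without blunting (+0.04 to +0.05 against +0.90 at 6 months). It could become negative if maternal antibody blunts the response as the protocol describes.

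The sample status follows from the documents. The sizes rest on assumed titre spread, half-life and blunting. The +0.90 benchmark is itself conditional: the protocol allows that most infants may have no detectable antibody at 6 months, which would weaken that correlation too. The right samples are in the design, and the primary comparison is unaffected. The line should be corrected before analysis.

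**What to change.** In the secondary end-point list, replace the 9- and 11-month timing for this objective with the 6-month pre-vaccination sample, both arms pooled. Keep Arm B at 9 months as a supportive time point, with a stated method for values below the detection limit. Name the same visit in the matching item of the Data Analysis list.

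Relate mothers' antibody to Arm A's 9-month titres and to all 11-month titres only under the separate item on vaccine response.

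The cost is a line of wording in each place. No new sample is needed. Pooling the arms gives up to 310 + 310 = 620 pairs, fewer where mothers decline blood sampling, since their infants may still be enrolled.
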